12.3 Response Criteria

12.3.1 Evaluation of target lesions

- Complete response (CR) – Disappearance of all target lesions. Any pathological lymph nodes (whether target or non-target) must have reduction in short axis to <10 mm.

- Partial response (PR) – At least a 30% decrease in the sum of diameters of target lesions, taking as reference the baseline sum diameters.
- Progressive disease (PD) – At least a 20% increase in the sum of diameters of target lesions, taking as reference the smallest sum on study (this includes the baseline sum if that is the smallest on study). In addition to the relative increase of 20%, the sum must also demonstrate an absolute increase of at least 5 mm. (Note: the appearance of one or more new lesions is also considered progression).

Patients with a global deterioration of health status requiring discontinuation of treatment without objective evidence of disease progression at that time should be reported as “symptomatic deterioration.” Every effort should be made to document the objective progression even after discontinuation of treatment.

- Stable disease (SD) - Neither sufficient shrinkage to qualify for PR nor sufficient increase to qualify for PD, taking as reference the smallest sum diameters while on study.

12.3.2 Evaluation of non-target lesions

- Complete response (CR) – Disappearance of all non-target lesions and normalization of tumor marker level. All lymph nodes must be non-pathological in size (<10 mm [<1 cm] short axis).
- Non-CR/Non-PD – Persistence of one or more non-target lesion(s) and/or maintenance of tumor marker level above the normal limits.
- Progressive disease (PD) – Appearance of one or more new lesions and/or unequivocal progression of existing non-target lesions. Unequivocal progression should not normally trump target lesion status. It must be representative of overall disease status change, not a single lesion increase.

Although a clear progression of “non-target” lesions only is exceptional, the opinion of the treating physician should prevail in such circumstances, and the progression status should be confirmed at a later time by the review panel (or Principal Investigator).

12.3.3 Evaluation of best overall response

The best overall response is the best response recorded from the start of the treatment until disease progression/recurrence. The reference for progressive disease is the smallest measurement since treatment initiation. The best response assignment will depend on the achievement of both measurement and confirmation criteria, as seen in the tables below, excerpted from the RECIST v1.1 manuscript ¹⁹.

For patients with measurable disease

Target Lesions	Non-Target Lesions	New Lesions	Overall Response	Best Overall Response when Confirmation is Required*
CR	CR	No	CR	≥4 wks. Confirmation**

CR	Non-CR/Non-PD	No	PR	≥ 4 wks. Confirmation**
CR	Not evaluated	No	PR	
PR	Non-CR/Non-PD/not evaluated	No	PR	
SD	Non-CR/Non-PD/not evaluated	No	SD	Documented at least once ≥ 4 wks. from baseline**
PD	Any	Yes or No	PD	no prior SD, PR or CR
Any	PD***	Yes or No	PD	
Any	Any	Yes	PD	

* See RECIST 1.1 manuscript for further details on what is evidence of a new lesion.
** Only for non-randomized trials with response as primary endpoint.
*** In exceptional circumstances, unequivocal progression in non-target lesions may be accepted as disease progression.

Note: Patients with a global deterioration of health status requiring discontinuation of treatment without objective evidence of disease progression at that time should be reported as "*symptomatic deterioration*." Every effort should be made to document objective progression even after discontinuation of treatment.

For patients with non-measurable disease (i.e. non-target disease)

Non-Target Lesions	New Lesions	Overall Response
CR	No	CR
Non-CR/non-PD	No	Non-CR/non-PD*
Not all evaluated	No	not evaluated
Unequivocal PD	Yes or No	PD
Any	Yes	PD

* 'Non-CR/non-PD' is preferred over 'stable disease' for non-target disease, since SD is increasingly used as an endpoint for assessment of efficacy in some trials, so to assign this category when no lesions can be measured is not advised

12.3.4 Duration of response

- Duration of overall response – The duration of overall response is measured from the time measurement criteria are met for CR or PR (whichever is first recorded) until the first date that recurrent or progressive disease is objectively documented. The duration of overall CR is measured from the time measurement criteria are first met for CR until the first date that progressive disease is objectively documented.

- Duration of stable disease - Stable disease is measured from the start of the treatment until the criteria for progression are met, taking as reference the smallest measurements recorded since the treatment started, including the baseline measurements.

12.3.5 Progression-Free survival

- Progression-free survival defined as the time between the date of first treatment and the date of first documented progression or death due to any cause, whichever occurs first.

[figure not shown]
12.3.6 Overall survival

- Overall survival is defined as the time between the date of first treatment and the date of death due to any cause. Patients who are alive will be censored at the time of the last follow-up.

13.0 Tissue and Blood Collection and Biomarker Studies

Correlative studies will be carried out at UPMC Hillman Cancer Center by [name] and at Emory Winship Cancer Institute in the laboratory of [name]. The majority of samples will be processed at and preserved at UPMC. All samples will be banked at UPMC as the central site of the study. See schema below regarding time of patient samples:

A Phase I/II Study of PI3K δ inhibitor Duvelisib in Combination with Nivolumab in Patients with Advanced Unresectable Melanoma who have Progressed on Anti-PD1 Therapy

13.1 Phase I Correlative Studies

For the phase I dose escalation study, patients will have blood drawn and tumor biopsies at baseline and again after 12 weeks of treatment. These time points were chosen based on prior experience with checkpoint inhibitors and duvelisib, as well as for patient convenience (monthly visits) and to correlate

with efficacy evaluations (every 12 weeks). We will also conduct a peripheral blood draw at 4 weeks. Previous analysis of peripheral blood samples in melanoma patients being treated with checkpoint inhibitors have demonstrated expansion of CD8+ T cells detectable as early as 4 weeks²⁴. Further, changes in peripheral cytokine levels have been seen as early as day 8 in lymphoma patients treated with duvelisib¹⁴. While evaluation at 4 or 12 weeks may not capture the “peak” of change with this therapy, we anticipate alterations attributable to therapy will be observed and can be correlated with outcomes in a clinically meaningful way.

We will use CyTek flow cytometry to evaluate peripheral blood mononuclear cells (PBMCs) and tumor-infiltrating cells from patients treated with each dose level of duvelisib. Several of the immune cell types that correlate with anti-tumor response, including CD8+ T cells, B cells and MDSCs, have been shown to be altered with PI3K γ or PI3K $\gamma\delta$ inhibition^{15, 14}. In particular, CD8+ T cells are often cytotoxic to tumor cells, and increased CD8+ TILs correlate with improved survival in patients with melanoma²⁵. Proliferation of intratumoral CD8+ T cells after immunotherapy was shown to correlate with anti-tumor response²⁴. The ideal RP2D will demonstrate proliferation and activation of CD8+ TILs. We will also examine CD8+ and CD4+ T cell subsets, and markers of activation and exhaustion by flow cytometry. Additional cell types of importance in the tumor microenvironment will also be queried, including T regulatory cells, B cells and monocyte precursors in peripheral blood and tumor biopsies.

Further, we will use RNA from PBMCs to evaluate the immune profile of patients prior to and on therapy with duvelisib with the Nanostring platform. This includes a panel of 770 genes associated with inflammation and autoimmune disease. Nanostring signatures will be correlated with any clinical toxicities observed, as a way to evaluate possible biomarkers of toxicity.

Along with toxicity data from the clinical portion of the phase I trial, this data will also help inform the recommended phase 2 dose of duvelisib. Ideally, the chosen dose will minimize patient toxicity while maximizing anti-tumor immune profile (high T effector cells, low T regulatory cells, low myeloid-derived suppressor cells). Observations from this portion of the study will be used to focus studies in the Phase II portion of exploratory analysis.

13.2 Phase II Correlative Studies

Patients enrolled in the phase II cohort will have blood draws at baseline and 12 weeks on treatment. Tumor biopsies will be performed at baseline and after 12 weeks on treatment. For the phase II correlative studies, we will use a multi-level approach to evaluate the interplay of the immune system with the tumor microenvironment (pre-treatment, post-treatment with duvelisib, and at progression). Studies will be focused on answering several questions pertinent to the mechanism of action of duvelisib and resistance to PD1 therapy.

First, we will characterize T cell responses to duvelisib. In combination with data from flow cytometry in Phase I studies, and we will add more detailed studies to characterize T cell activation through functional assays. We will also use Cytek to evaluate markers of T cell exhaustion, including LAG3, TIM3, TIGIT, CD38, bcl2 and HLA-DR. This data will be corroborated with a Nanostring T cell characterization panel which evaluates RNA expression of pathways involved in T cell activation, exhaustion, persistence, and metabolism. T cell metabolism will also be evaluated by an assay for mitochondrial mass.

Second, we will evaluate changes in the tumor microenvironment while on duvelisib using tumor biopsy samples. We will use flow cytometry to evaluate immune populations within tissues and evaluate whether these reflect changes in the periphery. Multispectral immunofluorescence will be used to evaluate the spatial relationship and interplay between immune populations, particularly between pro-inflammatory and anti-inflammatory populations. Presence and alterations of B cells in biopsy samples are of particular interest, given the known activity of duvelisib on B cells and the prognostic implications of B cells and tertiary lymphoid structures.

Finally, global changes in the tumor microenvironment will be evaluated by single cell RNAseq. For these studies, fresh tissue from 9 patient's tumors with matched peripheral blood samples will be used. In addition to providing important data regarding alterations associated with duvelisib, these samples will also be informative regarding acquired resistance to anti-PD1 therapy.

The following techniques will be used:

Single cell RNAseq: We will perform single cell RNAseq on patient PBL and TIL pre and post treatment to assess effects on all immune populations for 9 patients who demonstrate a standard pattern of anti-PD1 resistance. This will generate a robust data set that could give us information on differences that would not be detected by the above methods. Further, because we will utilize the 10x 5' system, we could ideally get both RNA signatures as well as paired TCR and BCR sequences from these patients.

Cytek Aurora (26 parameter flow cytometry): Via the UPMC Hillman Cancer Cytometry Facility, we will utilize the Cytek Aurora to analyze changes in immune cells pre and post therapy. We will be able to analyze samples with three comprehensive, 26 parameter panels which will assay general changes in the immune infiltrate (unbiased, analyzing all populations) as well as specific changes in CD8+ T cells, Tregs, macrophages and B cells, given the specific effects of this therapeutic regimen described in the literature.

Multispectral IF: We will pair our above flow cytometric analyses with locational studies on the immune infiltrate via Vectra Polaris multispectral IF (7 colors in total). Further, we will expand our panels to an Akoya CODEX system able to assay 30+ biological correlates on a single piece of paraffin embedded tissue.

In vitro functional assays: The [name] lab has developed micro-sized functional assays that can assess CD8+ T cell, Treg, macrophage and B cell function pre and post treatment, which will be used to analyze Study specimens.

Nanostring: RNA Analysis of 770 gene panel for evaluation of multiple aspects of T cell biology, including activation, metabolism and exhaustion will be employed. A separate panel will be used to evaluate RNA signatures in toxicity which includes genes involved in inflammation and autoimmunity.

14.0 Statistical Methods

This clinical trial includes a phase I dose-finding study and a phase II efficacy study. The phase I portion requires up to 18 patients. The phase II portion needs an additional 24 patients (6 carried over from phase I using the RP2D level) for a study total of up to 42 patients and a phase II total of 30 patients. With 2 centers, each accruing 1-2 patients per month, we anticipate completing enrollment in 18 months.

14.1. Phase I Portion of the Study

14.1.1. Study Design

The primary objectives of the phase I portion are to determine the maximum tolerated dose (MTD) of duvelisib when combined with anti-PD1 therapy nivolumab, and to decide on its recommended phase II dose (RP2D). Dose escalation will follow the decision rule in the following table, using the three dose levels defined in Section 7.5 (i.e., 15mg Daily, 25mg Daily, and 25mg BID), starting from the lowest dose. The MTD is defined to be the highest dose level at which no more than 1 of 6 treated patients experiences a DLT (DLT is defined in Section 8.1). Cohorts of three to six patients each will be treated at a dose level. Patients should have taken 75% of pills to be included in analysis of their respective cohort, as assessed through pill counts and pill diary. Only toxicities observed during the first treatment cycle will affect dose escalation. Late toxicities observed will be discussed at monthly data safety monitoring boards to determine if dose adjustments should be made.

After MTD is determined, we will decide on RP2D based on an overall consideration of DLT data, as well as immune cell profiling with laboratory correlates. For this purpose, our decision rule in the following table is a slight modification of the standard “3+3” to make sure 6 patients will be accrued at each safe dose in order to have enough patients for laboratory evaluations. RP2D should not be higher than MTD. If the MTD is not reached, RP2D will be decided based on safety data from acute and late toxicities as well as immune cell profiling data by the investigators (see section 13.1).

DECISION RULES FOR DOSE LEVEL ESCALATION

No. of patients with DLT's at this dose level	No. of patients treated at this dose level	Action
≤1	3	Treat 3 more patients at this dose level.
≤1	6	Treat 3 patients at the next higher dose level (or if at the highest level, stop the trial, and declare the dose at this level to be the MTD).

>1	3 or 6	Stop dose escalation. The previous dose is defined as MTD.
----	--------	--

Cohorts need not be completed if clear decisions can be made on the basis of an incomplete cohort. For example, if the first two patients in an intended cohort of three experience DLT's, escalation can be stopped without accruing the third member of the cohort.

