8.1 Dose Limiting Toxicities

Acute dose limiting toxicities (DLTs) are defined as any of the following AEs and laboratory abnormalities considered possibly, probably, or definitely related to study treatment that occur any time from the initial dose of duvelisib in combination with nivolumab through day 28 of treatment. Toxicities occurring from day 29 through 28 days after completion of treatment will be considered late toxicities. Only acute DLTs will be considered for decisions to continue enrollment at the current dose level or proceed to the next dose level. Acute and late toxicities will be considered when deciding on the RP2D and will be discussed in monthly Data Safety Monitoring Board (DSMB) meetings. See Section 15.0 for further details.

Severity of adverse events will be graded by National Cancer Institute Common Terminology Criteria for Adverse Events version 5.0 (CTCAE v5.0). A goal of $\leq 33\%$ DLTs at each dose level will be considered acceptable.

Whenever possible, biopsies are recommended if they can be done safely to help determine between immune-related and other etiologies of toxicity, particularly for rash and colitis. Biopsies for elevated liver enzymes and/or for pneumonitis should be considered if deemed feasible and safe in the context of risk:benefit evaluation. General criteria for consideration of biopsy:

- Diarrhea/colitis
 - Biopsy proven grade ≥ 3 immune-related colitis
 - Diarrhea of grade ≥ 3 that does not respond to treatment with steroids within 5 days
- Pneumonitis
 - Immune-related pneumonitis grade ≥ 2

- Any grade ≥ 3 pneumonitis
- Hematologic abnormalities
 - Neutropenia grade 4 despite holding duvelisib for 7 days
 - Thrombocytopenia grade ≥ 3 with bleeding
 - Thrombocytopenia grade 4
- Other immune-related toxicities
 - Any grade ≥ 3 toxicity that does not respond to treatment within 5d
- For the remainder of non-hematologic toxicities, grade ≥ 3

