12.1 Definitions

- **Evaluable for toxicity** – All patients are evaluable for toxicity upon initiating treatment of nivolumab and duvelisib. For the phase I portion, patients should have taken 75% of duvelisib pills according to pill diary and pill counts.
- **Evaluable for objective response** – Patients who have measurable disease at baseline and have their disease re-evaluated at 12 weeks of therapy will be evaluable for response. Patients who

exhibit objective disease progression prior to the end of cycle 1 will also be considered evaluable.

- **Evaluable non-target disease response** – Patients who have baseline lesions that are evaluable but do not meet the definitions of measurable disease have received at least one cycle of therapy and have had their disease re-evaluated will be considered evaluable for non-target disease. The response assessment is based on the presence, absence, or unequivocal progression of the lesions.
- **Measurable disease** – Tumor lesions that can be accurately measured by the longest diameter in the plane of measurement with a minimum size of 10mm by CT scan, 10mm caliper measurement on clinical exam, 20mm by chest x-ray. CT scan thickness should be no greater than 5mm. Tumor measurements must be recorded in mm or decimal fractions of centimeters.
- **Malignant lymph nodes** – To be considered pathologically enlarged and measurable, a lymph node must be $\geq 15\text{mm}$ in short axis when measured by CT scan. Only the short axis will be measured and followed.
- **Non-measurable disease** – All other lesions, including small lesions $< 10\text{mm}$ and lymph nodes $< 15\text{mm}$ are considered non-measurable disease. Other non-measurable disease examples include ascites, pleural or pericardial effusion, lymphangitic involvement of skin or lung, abdominal masses/abdominal organomegaly that don't correlate to CT or MRI, bone lesions, inflammatory breast disease.

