14.1.2. Sample Size/Accrual Rate

The number of patients accrued to the study will depend on the MTD. No more than 18 evaluable patients will be treated in the phase I portion. An evaluable patient is defined as one who either a) receives at least one dose the study drug and/or suffers DLT, or b) completes a treatment cycle and has no DLT observed during this cycle.

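### Phase I has conflicting rules on who counts for dose escalation, and the 75%-of-pills condition makes no exception for a patient with a DLT

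*Combined protocol and SAP*

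**What the plan says.** Four statements bear on who enters the phase I escalation decision.

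- **Section 14.1.1**, between the MTD definition and the decision table: "Patients should have taken 75% of pills to be included in analysis of their respective cohort, as assessed through pill counts and pill diary".
- **Section 12.1**, definition of evaluable for toxicity: "All patients are evaluable for toxicity upon initiating treatment of nivolumab and duvelisib". The next sentence adds: "For the phase I portion, patients should have taken 75% of duvelisib pills according to pill diary and pill counts".
- **Section 14.1.2**, limb (a) of the definition of an evaluable patient: "receives at least one dose the study drug and/or suffers DLT". Limb (b) is a completed cycle with no DLT. Neither limb has a pill threshold. The same section caps phase I at 18 evaluable patients.
- **Section 14.1.1**, MTD rule: the highest dose at which "no more than 1 of 6 treated patients experiences a DLT". The columns of the decision table also count patients treated at the dose level.

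Section 8.1 sets the DLT window from the first combination dose through day 28, and adds: "Only acute DLTs will be considered for decisions to continue enrollment at the current dose level or proceed to the next dose level".

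**The concern.** These rules select different patients, and no passage says which one governs. A compliance condition is reasonable for a patient without a DLT, because someone who took little drug says little about its safety. It is a problem when applied to a patient with a DLT. Table 7.6 withholds or discontinues duvelisib for many severe events, so the toxicity itself can push pill intake below the threshold. A rule with no DLT exception can then remove the event that the table is there to count.

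Section 14.1.2 has a separate weakness in the opposite group. If *and/or* is read as *or*, a patient who takes one dose and leaves without a DLT is evaluable and counts as DLT-free. Limb (b) then adds nobody whom limb (a) has not already admitted.

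The MTD and RP2D are the phase I primary endpoints, and the RP2D may not exceed the MTD. With a limit of 1 in 6, a single inclusion decision can change the result.

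**Working it through.** **The plan's own totals.** 3 dose levels × 6 patients = 18. 18 + 24 = 42 in all. 24 + 6 carried over = 30 in phase II. All agree with Section 14.0.

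**What 75% means if the denominator is planned pills over 28 days (an assumption; neither sentence states it).** 0.75 × 28 = 21 daily capsules, or 0.75 × 56 = 42 twice-daily capsules. More than 7 days off drug fails.

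**How each rule treats typical patients, on that denominator**

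| Patient | 75% sentences | Section 14.1.2 | Treated count |
|---|---|---|---|
| DLT, duvelisib stopped after day 10 (10/28 = 36%) | Out | In | In |
| DLT after a 7-day hold (21/28 = 75%) | In | In | In |
| DLT with 8 days missed (20/28 = 71%) | Out | In | In |
| One dose, leaves, no DLT | Out | In if *or*; out if *and* | In |
| Completes cycle, no DLT, under 75% | Out | In, limb (b) | In |

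**The neutropenia item.** Section 8.1 lists "Neutropenia grade 4 despite holding duvelisib for 7 days". The list stands under a sentence about considering biopsy, although Section 14.1.1 cites 8.1 for the DLT definition. The 7-day hold uses the whole 25% allowance but still meets the rule. Exclusion needs at least one more missed day.

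**Effect on one decision.** Take six treated patients with two DLTs, one of them stopped after day 10.

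- Counting treated patients, or under Section 14.1.2: 2 of 6, so escalation stops.
- Under the literal 75% rule: 1 of 5. The table has rows for 3 and 6 patients only, so no action is defined.
- If a DLT-free replacement were then added, which no passage provides for: 1 of 6, and the dose escalates.

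**Illustrative pass probabilities.** Let p be the true DLT rate and f the share of DLT patients excluded and replaced. The documents do not give f.

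Counted DLT rate: q = p(1 − f)/(1 − pf).

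P(pass) = P(at most 1 DLT in 6) = (1 − q)^6 + 6q(1 − q)^5. The two-stage form in the table (at most 1 in 3, then at most 1 in 6) gives the same value.

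For p = 0.40 and f = 0.25: q = 0.30/0.90 = 0.333, so P = 0.088 + 0.263 = 0.351.

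| True DLT rate p | f = 0 | f = 0.25 | f = 0.50 |
|---|---|---|---|
| 1/3 (the acceptable limit in 8.1) | 0.351 | 0.481 | 0.655 |
| 0.40 | 0.233 | 0.351 | 0.534 |
| 0.50 | 0.109 | 0.191 | 0.351 |

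**The *or* reading of 14.1.2 at p = 0.40.** If k of six leave early and count as DLT-free, P(pass) = P(at most 1 DLT in 6 − k). This is 0.337 for k = 1 and 0.475 for k = 2, against 0.233 for k = 0. The values of k are also assumptions.

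**The case against.** The strongest reply is that most of the text already counts the early DLT. The MTD rule and the table say *treated*. Section 12.1 opens by making everyone who starts treatment evaluable for toxicity. Limb (a) of 14.1.2 admits any patient with a DLT. The example under the table, "if the first two patients in an intended cohort of three experience" DLTs, allows escalation to stop with no pill check. The 75% sentences say only *should*. To lose a DLT, the team would have to let that wording override the rest and also take planned pills as the denominator. To escalate as a result, it would also have to add a replacement. This is a fair account of the probable intent, and it stands. It does not remove the conflict, because the 75% sentence sits in the same section as the table and states a condition for inclusion in the cohort's analysis.

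The denominator is also open. The diary in Appendix B has a field for the pills that should have been taken. If that means pills due after protocol holds, few DLT patients or none might be excluded. If pills from the optional two-week lead-in in Section 7.5 counted, a 7-day hold would leave 35/42 = 83%. Nor does every listed toxicity cost pills: Table 7.6 leaves duvelisib unchanged for grade 3 thrombocytopenia with grade 1 bleeding.

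Finally, the DSMB and DSMC review serious adverse events and can suspend accrual, and the RP2D also draws on late toxicity and immune profiling. These limit the harm, but they do not say who belongs in the table.

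**Conclusion.** The point stands as an unresolved conflict between inclusion rules that feed a primary endpoint, and it should be fixed. The conflict is certain from the text. Its effect on escalation is not known. The one-patient example shows that the answer can change from stopping to a count with no defined action.

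A reader might go further in four ways that the documents do not support:

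- That the plan directs early DLTs to be discarded. Most of its wording points the other way.
- That the neutropenia item proves exclusion on its own. A 7-day hold gives exactly 75%, which passes.
- That pass rates are inflated by a known amount. The exclusion share, the denominator and replacement are all assumptions, and if f is near 0 the first column of the pass table applies. The onset medians of 3 to 4 months in Sections 11.1 to 11.4 come from earlier duvelisib experience and give no basis for choosing f within 28 days.
- That Section 14.1.2 drops DLTs. It drops none. Its fault is that it may admit uninformative DLT-free patients.

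**What to change.** Use one DLT-evaluable definition in Sections 12.1, 14.1.1 and 14.1.2, the MTD rule and the decision table:

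1. Any patient with a DLT in the 28-day window counts, whatever share of pills was taken.
2. A patient without a DLT counts only after completing the 28-day window with at least 75% of the planned 28-day duvelisib pills.

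Remove the one-dose *and/or* wording from limb (a) of 14.1.2. State that patients who meet neither condition are replaced for DLT assessment but stay in safety reporting. Make the expected-pill field in Appendix B use the same denominator. Section 14.1.2 already expresses its cap of 18 in evaluable patients, so align the totals of 18 and 42 in Section 14.0 with that wording.

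The cost is a short wording amendment and possibly one or two replacement patients, since a DLT-free patient with more than 7 days off drug would no longer count.
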